Methodology	Qualitative: Cognitive Interviewing
Study Duration	1 hour
Study Center(s)	Single-center
Objectives	Validation of clinician reported measures of pediatric sedation
Number of Subjects	24
Diagnosis and Main Inclusion Criteria	Pediatric anesthesiologists and pediatric critical care physicians will be enrolled
Statistical Methodology	Qualitative: Thematic Analysis

CONFIDENTIAL

This document is confidential and the property of the Duke University.
Version 1.0 Date: 28 March 2019

1 Introduction

This document is a protocol for a human research study. This study is to be conducted according to US and international standards of Good Clinical Practice (FDA Title 21 part 312 and International Conference on Harmonization guidelines), applicable government regulations and Institutional research policies and procedures.

1.1 Background

Anesthesia and analgesia are increasingly recognized as integral parts of inpatient and outpatient management of infants, children, and adolescents.¹ However, many anesthetics and analgesics are not approved by the US Food and Drug Administration for use in children due to inadequate information on drug efficacy, safety, and dosing in pediatric populations.^{2,3} In order to assure optimal pharmacotherapy, it is imperative to select the correct drug dose. The Pediatric Trials Network (PTN) seeks to complete safety and efficacy studies of understudied but commonly-administered anesthetics to children. The studies will help define an optimal dosing regimen for pediatric populations. In order to complete these studies and submit data to the US FDA for update of pediatric labeling, the PTN requires outcome measures for sedation levels that have been thoroughly validated. Existing clinician report pediatric sedation scales do not have adequate qualitative evidence to support content validity for any of these scales to be used as outcome measures.

This Study

This study will conduct qualitative interviews to provide evidence for the content validity and comprehension of existing physician-reported measures of sedation levels of children receiving anesthesia to facilitate a diagnostic or surgical procedure. Information gained from this study will inform the use of the measure in studies that are part of the PTN.

2 Study Objectives

Primary Objective

To assess the content validity and physician understanding of the Pediatric Sedation State Scale (PSSS) and the University of Michigan Sedation Scale (UMSS) via cognitive interviewing methods.

3 Study Design

3.1 General Design

This is a qualitative, questionnaire validation study using 1 hour, phone-based cognitive interviews with pediatric anesthesiologists and pediatric critical care physicians. Participation will last for the duration of the 1 hour phone interview.

3.2 Primary Study Endpoints

The two co-primary study endpoints are physicians' 1) comprehension of items and response options on clinician reported pediatric sedation scales, and 2) evaluation of the relevance of the scale to capture sedation levels.

CONFIDENTIAL

This document is confidential and the property of the Duke University.
Version 1.0 Date: 28 March 2019

4 Subject Selection and Withdrawal

4.1 Inclusion Criteria

1. Is a practicing clinician in a clinical care environment
2. Cares for pediatric patients >50% of their time
3. Treats or works with pediatric patients who are sedated/anesthetized for diagnostic and/or therapeutic procedures
4. Holds one of the following titles/positions
 - a. Anesthesiologist
 - b. Pediatric critical care physician
 - c. Clinical pharmacist (PharmD)
 - d. Nurse anesthetist
 - e. Nurse practitioner
 - f. Physician assistant
 - g. Nurse (with a BSN/RN or higher)
5. Is over the age of 18 years
6. Can speak English
7. Is capable of giving informed verbal consent

4.2 Exclusion Criteria

1. Lack of access to a telephone for interview

4.3 Subject Recruitment and Screening

Participants will be recruited via phone and email.

Emails will be sent to clinicians by Pediatric Trials Network (PTN) staff members and study staff. The email will contain brief information about the study (recruitment materials), a Study Information Sheet attachment (in place of a consent form with approval of a waiver of documentation of informed consent), and contact information for study personnel. Clinicians interested in participating may use the information in the email to contact study personnel.

Phone calls will be made by study staff to PTN member clinicians. An approved IRB phone script will be used by study staff making calls to potential participants.

Because clinicians are busy, we expect that recruitment for the study will require a number of contacts before we can schedule physicians for the interview. We will keep a list of any clinicians who refuse participation so that they will not be subsequently contacted during the recruitment period.

Study staff will review the Study Information Sheet with potential participants, answer any questions the clinician has about the study, and screen interested clinicians for eligibility using self-reported information obtained over the phone or via email.

CONFIDENTIAL

**This document is confidential and the property of the Duke University.
Version 1.0 Date: 28 March 2019**

4.4 Subject Consent

Given the design and topic of this interview study (content validity and comprehension of clinician reported outcome measures of pediatric sedation), we believe this study qualifies for Exempt Research status under 45 CFR 46.104(d)(2)(ii) because:

- The research involves only the use of standard interview procedures; and
- We will have robust confidentiality protections in place to protect the data—but even in the unlikely event of participants' responses being disclosed in identifiable form, we do not believe participants would reasonably be placed at risk of criminal or civil liability or that the responses would be damaging to the subjects' financial standing, employability, or reputation. Our topic is neither personal nor sensitive, and the questions posed to participants are intended to ascertain whether the design of a survey is adequate to assume content validity and comprehension of survey items and responses by users of the questionnaire, not right or wrong answers.

This study does not involve patients; participants will be health care professionals. Participants will be provided with a Study Information Sheet that includes a brief description of the study objectives and procedures, along with information on data safety and confidentiality.

Agreement to participate in the survey and/or interview will serve as consent to participate in the study.

4.5 Early Withdrawal of Subjects

4.5.1 When and How to Withdraw Subjects

As this study is a qualitative interview study lasting for only 1-hour, we do not anticipate having to withdraw subjects from the study based on safety or non-compliance. However, there may be instances in which a participant needs to end the interview early. In these instances, we will work to schedule a new time to complete the interview within the following two weeks. If the interview cannot be scheduled for completion within 14 days, we will retain the already collected data from the participant and consider any uncollected data as missing.

5 Study Procedures

Participants will take part in a semi-structured qualitative interview (~1 hour).

One day before the interview, the participant will receive a reminder email with details about their phone interview time, the study information sheet, and three documents for use during the interview: Definitions (of sedation levels), Scale A (PSSS), and Scale B (UMSS).

At the start of the interview, the interviewer will ask the participant if they received the email with the attachments and ask them to pull the email up as the materials will be referenced during the interview. The interviewer will send a new copy of the materials if the participant cannot locate them.

CONFIDENTIAL

**This document is confidential and the property of the Duke University.
Version 1.0 Date: 28 March 2019**

Participants will then be given a demographic survey, which will be read aloud to them over the phone and completed by the interviewer based on answers given by the participant.

After the demographics survey, the interviewer will begin the interview using the interview guide. The interview will consist of cognitive interviewing questions related to the survey instructions and the surveys' items and response options on 2 different clinician report pediatric sedation scales, the Pediatric Sedation State Scale and the University of Michigan Sedation Scale.

Example questions may include:

1. Which scales have you previously used to measure sedation levels in your pediatric patients?
 - a. **[For any scale mentioned]**
 - i. How long have you used the [name of referenced scale]?
 - ii. What strengths do you think the [name of referenced scale] has?
 - iii. What limitations do you think the [name of referenced scale] has?
2. How clear are the scale instructions?
3. Looking at the sedation level categories in this scale, how clearly do you think each level is defined?
 - a. How distinct do you think each category's definition is from the others?
 - b. Are there any terms or phrases that are unclear or might create confusion when scoring a child on these levels?
 - c. Are they appropriate for pediatric patients in the following age ranges?
 - i. <2 year
 - ii. 2-6
 - iii. 6-12
 - iv. 12-18

At the conclusion of the interview, the interviewer will thank the participant for their time and send the participant the forms to complete for participant payment. Once forms are completed and returned, the interviewer will process an AP check request to have the participant paid.

6 Statistical Plan

6.1 Sample Size Determination

Cognitive interviewing seeks to assess the way in which questionnaire content is understood to ensure that what is expected to be measured is actually being measured. The type of logical and

CONFIDENTIAL

This document is confidential and the property of the Duke University.
Version 1.0 Date: 28 March 2019

structural problems that we wish to identify are relatively independent of sample size and approximately 5-15 interviews per round is a generally accepted guideline for cognitive interviews.⁴ Multiple rounds may be needed if questions need to be revised and retested. Our sample minimum sample size will be 18 and the maximum will be 24. This will provide a more than adequate sample size. Additionally, the sample will include a minimum of 2 anesthesiologists, 2 critical care physicians, and 2 nurses to ensure we obtain responses from a variety of clinical care professionals.

6.2 Statistical Methods

Qualitative research does not incorporate standard statistical methodology, but rather uses qualitative analysis methodologies. In this study, at least two analysts will independently review transcripts and debriefing forms. During the initial transcript reviews, transcripts will be double coded (the same transcript independently coded by two analysts) and coding results compared. This will continue until an inter-coder reliability of at least 90% is reached on double coded transcripts. After inter-coder reliability is reached, transcripts will be coded individually by only one analyst with the exception of every 6th transcript, which will be double coded to ensure the continuation of inter-coder reliability. Once review and coding is complete, we will create an item-tracking matrix to document changes to the measure, as well as reasons for those changes. A summary report will be compiled with our analysis, detailing our process and our findings from the cognitive interviews.

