8.1 Study Monitoring Plan

This study will be monitored via weekly data review meetings and quality control (QC) reviews of data files. Weekly data review meetings will include review of study operations including enrollment progress, recruitment issues, and review of data summaries from interviews completed in the previous week. Data summary reviews will include discussion of completeness of data, quality of data, and how effective the interview guides are at collecting the desired data. Weekly QC checks for the study will include checking that enrollment logs, participant identifiers for scheduling and for the "do not re-contact" list, all audio recordings, and all transcripts are stored in the appropriate folder on the secure DPHS server. Consent will be obtained verbally, so no consent form review will occur. All encrypted audio recorders will be checked weekly to ensure no audio files are left on them after being moved to the DPHS secure folder for this study. Additionally, the first 3 interview transcripts obtained on the study and 10% of subsequent transcripts will be checked to ensure that interviewers are not deviating from

CONFIDENTIAL

**This document is confidential and the property of the Duke University.
Version 1.0 Date: 28 March 2019**

interview scope and are completing interviews as planned. The investigator and Research Program Leader will allocate adequate time for such monitoring activities.

The investigator will permit study-related monitoring, audits, and inspections by the EC/IRB, the sponsor, government regulatory bodies, and University compliance and quality assurance groups of all study related documents (e.g. source documents, regulatory documents, data collection instruments, study data etc.). The investigator will ensure the capability for inspections of applicable study-related facilities (e.g. pharmacy, diagnostic laboratory, etc.).

Participation as an investigator in this study implies acceptance of potential inspection by government regulatory authorities and applicable University compliance and quality assurance offices.

9 Ethical Considerations

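### Does section 6.2 need a rule for returning to double coding after a failed every-6th check or at the start of a new interview round?

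*Combined protocol and SAP*

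**What the plan says.** Section 6.2 starts with full double coding. On when that ends it says: "This will continue until an inter-coder reliability of at least 90% is reached on double coded transcripts". From there, "After inter-coder reliability is reached, transcripts will be coded individually by only one analyst with the exception of every 6th transcript", and that sixth transcript is one "which will be double coded to ensure the continuation of inter-coder reliability". The section also states that "at least two analysts will independently review transcripts and debriefing forms". Once review and coding are finished, the team will build an "item-tracking matrix to document changes to the measure" and write a report setting out its process and findings.

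Section 6.1 sets the sample at 18 to 24 and cites the guideline that "approximately 5-15 interviews per round is a generally accepted guideline for cognitive interviews". It adds: "Multiple rounds may be needed if questions need to be revised and retested". Section 6.2 does not mention rounds.

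Section 8.1 has its own transcript check, on the first 3 transcripts and then a sample: "10% of subsequent transcripts will be checked to ensure that interviewers are not deviating from" the interview scope. That check concerns how interviews are conducted, not how they are coded.

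**The concern.** Read literally, 90% is a gate passed once. After it, the every-6th transcript is the only exception to single coding. Two situations then have no stated response.

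- **A check below 90%.** The text gives no reconciliation step, no return to double coding, and no review of the transcripts coded by one person since the previous check.
- **A round on revised questions.** If transcripts are coded in interview order, that round would open in single coding, on agreement reached with the previous wording.

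Section 1.1 says the network needs thoroughly validated sedation measures. A retest round would be the evidence for any changed wording, so unnoticed coder drift there would weaken what the study exists to supply.

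**Working it through.** The plan derives no figure here: 90% and every 6th are design choices. The useful check is how many transcripts are exposed and what the text supports.

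**Inputs.** N = 18 to 24, 5 to 15 interviews per round (section 6.1), and one check in every six transcripts (section 6.2). The plan does not say at which transcript, k, the 90% is reached; I assume k = 1 to 6. Nor does it say whether every 6th is counted from k or from the first transcript, so I use both.

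**Exposure over the study.** Single-coded = N − k − number of checks.

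| N | k | Count starts at | Checks at | Single-coded |
|---|---|---|---|---|
| 18 | 1 | k | 7, 13 | 18 − 1 − 2 = 15 |
| 18 | 3 | k | 9, 15 | 18 − 3 − 2 = 13 |
| 18 | 3 | first transcript | 6, 12, 18 | 18 − 3 − 3 = 12 |
| 18 | 6 | either | 12, 18 | 18 − 6 − 2 = 10 |
| 24 | 1 | k | 7, 13, 19 | 24 − 1 − 3 = 20 |
| 24 | 3 | k | 9, 15, 21 | 24 − 3 − 3 = 18 |
| 24 | 6 | either | 12, 18, 24 | 24 − 6 − 3 = 15 |

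That leaves 10 to 15 of 18, or 15 to 20 of 24, single-coded, with 2 to 4 checks. Five transcripts lie between consecutive checks, so a failed check puts about five in question. This saving in effort is what the plan chose.

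**Exposure in a later round.** A round of n transcripts holds floor(n/6) to ceil(n/6) checks: 0 or 1 for n = 5, 1 or 2 for n = 9, 2 for n = 12, and 2 or 3 for n = 15. Only a round of 5 can go wholly unchecked. A later round usually has a smaller double-coded share than the first, but not always. With k = 3 counted from k:

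- 12 + 12 interviews: transcripts 1, 2, 3 and 9, so 4/12, against 15 and 21, so 2/12.
- 14 + 7 interviews: 4/14 = 29%, against 15 and 21, so 2/7 = 29%.

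**What the text supports on a failed check.** The sixth-transcript coding is there to ensure that agreement continues. Ensuring asks more than recording a number. A team that sees agreement below its own threshold and carries on unchanged would not be meeting that purpose. Silence on the exact steps does not forbid them.

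**What the text supports on a new round.** The 90% condition attaches to double-coded transcripts, not to a question or scale version. The probes in the interview guide (clarity, distinctness, confusing terms, suitability by age) are nearly the same for two quite different scales, so codes built on them need not change when a phrase is edited. Section 6.2 places the matrix of changes after coding. If that is one pass, no later round on revised wording is shown being coded. If it is a cycle for each round, the initial reviews that are double coded can be read as the start of each round.

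**Would a fixed trigger help?** Suppose each check is judged alone on m independent coding units, m = 30 to 100, and true agreement is 92%, above the threshold. All of these are assumptions, and independence within an interview is doubtful. Let f = P(Bin(m, 0.92) < 0.9m). The chance of at least one failure in two checks is 1 − (1 − f)²:

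- lowest at m = 100: f = 0.176, giving 1 − 0.824² = 0.32
- highest at m = 39: f = 0.381, giving 1 − 0.619² = 0.62

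On these assumptions a mechanical per-transcript rule would often send adequate coders back to re-review. The figures do not predict what this study will see.

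**The case for a change.** The strongest case for a change is that the plan chose a numerical threshold and a schedule of checks, and then left out the one thing that makes a check useful, the consequence. That gap does not depend on how many rounds are run. Section 8.1 does not fill it, because its transcript check looks at interviewers and its weekly data review does not mention coder agreement. The independent review by two analysts, even if it continues throughout, does not restore a 90% comparison. A sentence or two would cost little.

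All of this is correct as a reading of the text. It establishes that an action rule is unwritten. It does not establish that the check is missing, that coders would ignore a poor result, or that a finding would differ. The new-round part is weaker: it needs a second round that is only possible, a coding order the plan does not state, and the premise that agreement lapses when wording changes, which the plan nowhere says.

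**Conclusion.** No change to the plan follows. Section 6.2 does not spell out the response to a check below 90% or the coding mode at the start of a further round. Its stated purpose for the check already points analysts to reconcile and restore agreement, and the process is to be described in the final report. About five single-coded transcripts are at issue per failed check, out of 18 to 24, in a qualitative analysis with no hypothesis test or estimate to distort. Only a later round of 5 could lack any double coding. The judgement rests on analysts treating the check as more than a formality, which is what its wording asks. The counts rest on the assumed range for k and, for later rounds, on coding in interview order.

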6.3 Subject Population(s) for Analysis

All participants enrolled into the study who complete phone interviews will be included in the study analysis.

7 Data Handling and Record Keeping

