To do this, we'll need to ask you about your clinical background. Answering these questions is completely voluntary. If you choose not to answer them, you will not be eligible to participate in this study.

Because this will be an exempt study, there will be a waiver of documentation of informed consent. Therefore, if you qualify for the study and agree to participate, your agreement to participate will be your consent to participate, and you will not sign a physical consent form. You will be sent a study information sheet that will include information about the study, risks, benefits, and confidentiality before the phone interview and you will be able to ask any questions before or at the beginning of the phone interview. The personal information you give me today will become part of our research records and will be reviewed by [name] and the research staff. Your name will be kept on a separate file on a secure server and will not be attached to the eligibility information. If you do not qualify for this study, or you choose not to participate, no information you give us today, except your name, will be kept. Your name will be kept through the end of recruitment for the study for people who are ineligible or do not wish to participate in the study. It will be deleted from our files once recruitment is over.

Would you like to continue with the screening questions?

[If no, thank them for their time and say goodbye. If yes, continue with script.]

Question	Eligibility Requirement
1. "Are you a practicing clinician in a clinical care environment?"	Yes
2. "Do you care for pediatric patients >50% of your time?"	Yes
3. "Do you treat or work with pediatric patients who are sedated/anesthetized for diagnostic and/or therapeutic procedures?"	Yes
4. Do you hold one of the following titles/positions? 
 a. Anesthesiologist b. Pediatric critical care physician c. Clinical pharmacist (PharmD) d. Nurse anesthetist e. Nurse practitioner f. Physician assistant g. Nurse (with a BSN/RN or higher) 	Yes
5. How old are you?	18 or older
6. Can you speak English?	Yes
7. Do you give verbal consent to participate in the study?	Yes

If not eligible: Unfortunately, you do not meet the criteria for our study, but we do appreciate your interest and time. Thank you.

If eligible: You are eligible for participation in this study.

If you are still interested in participating, do you have time now to schedule the interview?

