Version 1.0 Date: 28 March 2019**

22 Appendix I– Interview Guide – PSSS First

Protocol No.: Pro00102030Protocol Name: Pediatric Sedation Study

Date: _____

Participant ID: _____

Randomization Group: PSSS 1st UMSS 1st

Clinical Outcomes Assessments of Pediatric Sedation

Cognitive Interview Guide

Introduction

Thank you for taking the time to talk with me today. As we talk, I'm going to ask you questions about two Clinician Reported Outcome scales used to assess sedation level in pediatric populations from birth up to 18 years of age. The questions we ask during this interview will help us to assess the clarity / comprehension of response options for each scale and evaluate the ability of the scale to validly capture different sedation levels. We are particularly interested in how the scales perform for assessing sedation levels related to diagnostic and therapeutic procedures.

I'm here to learn from you during this interview. There are no right or wrong answers and everything you say in this interview will be kept confidential. Our discussion will last about an hour and your participation in this interview is completely voluntary. If at any time you need to stop the interview, just let me know. As a busy clinician, we know that things may come up, so if we do need to end the interview early, but you wish to reschedule to complete the interview in the next 2 weeks, let me know that as well.

Before we get started, I just need to verify that you received our reminder email yesterday and that you have a copy of the materials needed for the interview today. You should have 4 attachments. We will use three of them in the interview: the definitions file, the Scale A file, and the Scale B file. Do you have these materials or should I send you a new copy now? [Send files if needed.]

[If previously agreed to audio recording]

Lastly, as we discussed earlier, I will be audio recording our conversation. I just want to check in and confirm that audio recording the interview is still fine with you.

Yes

Great. I'll start the recorder now.

No

Okay. Instead of audio recording, I'll take detailed notes. I will be writing a lot and may need to pause between questions, but I want you to know that I am listening to you even when I am writing. Let's get started.

[If previously refused audio recording]

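### Does the analysis population in section 6.3 shut out the unfinished interviews whose data section 4.5.1 keeps?

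*Combined protocol and SAP*

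**What the plan says.** Section 6.3 is the only statement of who is analysed: "All participants enrolled into the study who complete phone interviews will be included in the study analysis". It says no more about what counts as complete.

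Section 4.5.1 foresees that a clinician may have to stop early and plans to book a second call within two weeks. "If the interview cannot be scheduled for completion within 14 days", the rule is that "we will retain the already collected data from the participant and consider any uncollected data as missing". The interview guides (both labelled Appendix I) make the same offer to the participant: "if we do need to end the interview early, but you wish to reschedule to complete the interview in the next 2 weeks".

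Two other sections bear on the point without settling it. Section 6.2 says that "at least two analysts will independently review transcripts and debriefing forms" and does not distinguish finished from unfinished interviews. Section 8.1 plans a weekly "review of data summaries from interviews completed in the previous week", including "discussion of completeness of data, quality of data".

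**The concern.** In section 4.5.1 and in the interview guides, to complete an interview means to finish one that was cut short. If that meaning is carried into 6.3, a clinician who stopped early and could not be rebooked falls outside the analysis population, although 4.5.1 has just said that the data are kept. Neither section refers to the other, so two analysts could each claim to follow the protocol and build different sets of transcripts.

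What would be lost is evidence on the first co-primary endpoint, comprehension of items and response options (section 3.2). The guides run in a fixed order: definitions and prior use, first scale, second scale, comparison, mapping. A clinician who stops after the first scale has already discussed how clear and distinct its levels are, which terms confuse, and how well it fits each age range. In cognitive interviewing a single participant can expose a wording fault, and under the narrow reading that fault would not reach the item-tracking matrix in section 6.2.

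**Working it through.** The plan states no figure on this point to reproduce. The check is a comparison of texts, followed by some counts for scale.

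**Step 1. Does 6.3 exclude anyone?** It says who will be included. It does not contain the word *only*, and it names no group to be left out. It also has an ordinary purpose that has nothing to do with partial interviews. The phone script (Appendix D) tells the clinician that "if you qualify for the study and agree to participate, your agreement to participate will be your consent to participate", so a person can have consented before any interview takes place. Section 6.3 can be read simply as separating those who were interviewed from those who agreed and never were.

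**Step 2. What does 4.5.1 imply for analysis?** It has two parts: keep the collected data, and treat the uncollected data as missing. The first alone could mean storage only. The second is a statement about data handling, and it has little purpose if the whole participant is dropped, because nothing is then analysed for the missing part to be missing from. The natural sense is that the participant stays in with gaps.

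**Step 3. Is *complete* used consistently?** No. In 4.5.1 and the guides it means finishing. In 8.1, interviews described as completed are still checked for completeness of data, so a completed interview there may have gaps. This second use supports the inclusive reading of 6.3.

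**Step 4. Do the two sections fit together?** Yes. Section 6.3 gives the general population and 4.5.1 the specific rule for interviews cut short. The exclusive reading has to add a restriction that 6.3 does not state and set aside the natural sense of 4.5.1.

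**Step 5. How much does a partial interview hold?** Take a clinician who stops at the end of the first-scale block.

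| Guide | Main questions in the first-scale block | Later main question on that scale alone | Asked |
|---|---|---|---|
| PSSS first | 4, 5, 6 | 14 (mapping) | 3 of 4 |
| UMSS first | 4, 5, and the question on distinguishing levels (misnumbered 1) | 15 (mapping) | 3 of 4 |

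The question not reached maps the scale's levels to the sedation definitions, which bears on the second co-primary endpoint (relevance of the scale). The second-scale block, the comparison and the PSSS-to-UMSS mapping would also be missing. These are counts of questions, not shares of evidence.

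**Step 6. Scale.** Inputs from section 6.1: minimum 18 and maximum 24 participants. The share lost if *k* interviews were excluded is *k*/*n*. The documents give no rate of early endings, so *k* is an assumption.

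| *k* (assumed) | *n* = 24 | *n* = 18 |
|---|---|---|
| 1 | 1/24 = 4.2% | 1/18 = 5.6% |
| 2 | 2/24 = 8.3% | 2/18 = 11.1% |

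The loss arises only if an interview ends early, is not finished within 14 days, and is then excluded on the narrow reading. It affects the findings only if that clinician raised something no one else did.

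**The case for a change.** The best argument for amending 6.3 is that it would take one sentence and fix the rule before coding starts. If the sponsor means to analyse partial interviews, the section that defines the population should say so. Sections 6.2 and 7.3 do not fill the gap: the first does not mention partial transcripts, and the second only requires missing entries to be explained on the form. Which scale is lost also depends on the order group, so the numbers contributing would differ between scales.

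Much of this stands as a remark on drafting. The term is undefined, the cross-reference is absent, and *retain* taken alone could mean storage. It is also true that section 6.1 does not say whether partial interviews count toward the minimum of 18 or the minimum of 2 in each of three professions. A partial interview could be half of a professional group held at its minimum (1/2).

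It does not amount to a fault in the design or the analysis. No stated rule, applied as written, gives a wrong result. Rewording is also less simple than it looks. A rule that admits anyone with any interview data would leave open the case of a clinician who answered only the demographic survey, which is read aloud on the same call before the guide begins (section 5). Counts per interview section would be a helpful courtesy in the summary report, but the thematic analysis does not depend on them.

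**Conclusion.** The wording of 6.3 is loose, but no change to the plan is needed. With 4.5.1 beside it, an analyst has enough to do the sensible thing: code a partial transcript for the parts it covers and treat the remainder as missing. If the sponsor revises the document for other reasons, a cross-reference would be a harmless clarification.

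The size is probably small and cannot be computed: each affected interview is between 4.2% and 5.6% of the planned sample, and the number affected is unknown. A one-hour call with a 14-day window to finish gives no reason to expect many. Section 6.1 also holds that the problems sought depend little on sample size.

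This conclusion rests on two assumptions: that 4.5.1 governs analysis as well as storage, which is its natural sense, and that unfinished interviews are few. If many interviews ended early, the summary report would need to say how many clinicians had discussed each scale, but the reading of 6.3 would not change.
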